7.2 Patient Discontinuation/Withdrawal from the Study

- A patient may withdraw from the study at his/her own request or may be withdrawn at any time at the discretion of the investigator for safety, behavioral, compliance, or administrative reasons. However, unless there is a safety reason, the patient should remain in the study until the End-of-study Visit, even when off study treatment, to protect the integrity of the study and the patient's well-being.
- If the patient withdraws consent, the CRO may retain and continue to use any data collected before the withdrawal of consent.
- If a patient withdraws consent, he/she may request destruction of any samples taken and not tested, and the investigator or qualified designee must document this in the site study records.
- See the SoA for data to be collected at the time of patient discontinuation/withdrawal from the study. The reason for the patient's withdrawal from the study and the withdrawal date should be recorded in the eCRF.

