The first dose of study treatment will be administered 30 minutes to 6 hours prior to the scheduled start of surgery on the operative day (Day 0), and the second dose will be administered postoperatively the evening of the operative day. Beginning on Day 1, patients will receive study treatment BID for up to 10 days postoperatively (ie, Day 10). Every effort will be made to give the Day 1 morning dose approximately 12 hours after the Day 0 evening dose and to give all morning and evening doses from Days 1 to 10 at approximately 12-hour intervals. Note that duration of administration will be determined by the date on which the primary endpoint, GI2, is met or the date on which the discharge order is written, whichever occurs first, and will not exceed 10 postoperative days (excluding the postoperative dose on Day 0). Study treatment may be administered on the day of discharge. Details regarding study treatment administration are provided in [Section 6.1](#).

During the treatment period, procedures and assessments will be performed as specified in the Schedule of Activities (SoA) in [Section 1.3](#).

Patients will be discharged based on the clinical judgment of the investigator and standard of care at the study hospital. Patients who are discharged by Day 10 will have an End-of-study Visit 30 days after Day 10 or after the day of discharge (whichever is sooner), with a window of + 3 days, but not < 30 days.

Patients who discontinue study treatment prior to meeting the primary endpoint, GI2, will have an ET Visit and will be followed until 30 days after the day of discharge for safety. Patients who are withdrawn from the study will have an ET and an End-of-study Visit.

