7. DISCONTINUATION OF STUDY TREATMENT AND PATIENT DISCONTINUATION/WITHDRAWAL

7.1 Discontinuation of Study Treatment

A patient may discontinue study treatment prior to Day 10 if he or she meets the primary endpoint, GI2, or on the date on which the discharge order is written, whichever occurs first. Discontinuation of study treatment for any other reason will be determined by the investigator if he or she believes that it is in best interest of the patient. Female patients who become pregnant during the study will be followed as described in [Section 7.2](#), [Section 8.3.5](#), and [Appendix 4](#). The investigator will withdraw a patient from study treatment based on the management and discontinuation criteria for abnormal liver function tests ([Appendix 5](#)). The investigator should consider discontinuation of study treatment if opioid withdrawal is suspected on any assessment day. In addition, discontinuation of study treatment is required if:

- The patient has an unplanned ileostomy or colostomy during the surgical procedure.
- A patient has a score > 36 on the Clinical Opiate Withdrawal Scale (COWS) on any assessment day
- Hypersensitivity thought to be related to study treatment occurs and is considered severe in intensity, as assessed by the investigator
- There is any sign or symptom suggestive of gastrointestinal perforation, as assessed by the investigator

See the SoA for data to be collected at the time of treatment discontinuation (eg, at the Early Termination Visit).

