8.1 Efficacy Assessments

8.1.1 Primary Efficacy Assessments

8.1.1.1 Time from End of Surgery to Time to First Toleration of Solid Food and First Bowel Movement

The time from the end of surgery (defined as the time the patient leaves the operating room) to time to first toleration of solid food (defined as the time when the patient consumes a meal that requires chewing and has no significant nausea or vomiting, as per the judgment of the investigator, for 4 hours after that solid food) and first bowel movement (GI2) will be recorded in the eCRF. First toleration of solid food and first bowel movement will be recorded until the patient meets the primary endpoint described above. If the patient discontinues study treatment, the patient still needs to be followed for GI2 until the achievement of this endpoint or until he/she completes the study. If the patient is withdrawn from the study, first toleration of solid food and first bowel movement, as applicable, will be recorded at the ET Visit (see also [Section 9.4.5.1](#)). If a patient is discharged from the hospital prior to having a first bowel movement, the reason for discharge prior to having the first bowel movement will be recorded in the eCRF. Additionally, the patient will be instructed to inform the investigator or qualified designee by phone, text, or e-mail within 24 hours of having a first bowel movement up to and including Day 10. The investigator or qualified designee will communicate (phone, text, or e-mail) with the patient daily up to and including Day 10 to record when the first bowel movement occurred.

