9.4.5.1 Primary Efficacy Endpoint

The primary endpoint will be time from the end of surgery (defined as the time the patient leaves the operating room) to time to first toleration of solid food (defined as the time when the patient consumes a meal that requires chewing and has no significant nausea or vomiting, as per the judgment of the investigator, for 4 hours after that solid food) and first bowel movement (GI2).

The mean survival time, which is also referred to as the RMST, of GI2 events within 240 hours will be estimated using the area under the Kaplan-Meier (KM) curve. To demonstrate the linear dose-response relationship between treatment groups (3 naldemedine groups and placebo group) and the RMST, the linear contrast test for trend with contrast coefficients of (-3, -1, 1, 3) will be performed. If a dose-response relationship is detected, then pairwise comparisons of the RMST between each dose group of naldemedine and the placebo group will be conducted, and the treatment differences (with its 95% confidence interval [CI]) will be provided. If an event does not occur during the evaluation period of 240 hours, the patient will be censored at the time of his/her last nonmissing postbaseline assessment. The same analysis will be performed in the Per Protocol set. In addition, the reason for discharge prior to having the first bowel movement will be listed.

Patients will continue to be evaluated for efficacy regardless of treatment adherence. The use of additional therapies or interventions that could treat any component of the primary endpoint (eg, motility agents, anti-emetics, laxatives, etc), may confound the results of the primary efficacy analysis. This list of therapies will be finalized before database lock. To examine this issue, the following exploratory analyses of the GI2 endpoint will be performed or provided:

- Repeat of the primary analysis, excluding all patients who received additional therapies at any time postrandomization that could treat any of the components of the GI2 endpoint. It is recognized that this subset is selected based on postrandomization decisions, may be confounded with the treatment group, and may not represent a randomized subgroup of the primary endpoint.
- Table of proportion of patients in each treatment group who received additional therapies that could treat any of the GI2 components.

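### For a patient withdrawn from the study, including for safety, GI2 is recorded only up to the ET Visit and then censored, so unequal safety withdrawal across arms could bias the RMST contrast

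*Protocol*

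**What the plan says.** **Leaving the study.** Protocol Section 7.2 says a patient "may be withdrawn at any time at the discretion of the investigator for safety, behavioral, compliance, or administrative reasons". It then asks patients to stay, with one stated exception: "unless there is a safety reason, the patient should remain in the study until the End-of-study Visit, even when off study treatment".

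**Recording GI2.** Protocol Section 8.1.1.1 separates two cases. If the patient only stops study treatment, "the patient still needs to be followed for GI2 until the achievement of this endpoint or until he/she completes the study". For someone who leaves the study altogether, the rule is different: "first toleration of solid food and first bowel movement, as applicable, will be recorded at the ET Visit". Section 4.1 adds: "Patients who are withdrawn from the study will have an ET and an End-of-study Visit". No text says that GI2 is collected at that End-of-study Visit or between the two visits.

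**Analysis.** Under Protocol Section 9.4.5.1, when GI2 does not occur within 240 hours, "the patient will be censored at the time of his/her last nonmissing postbaseline assessment". SAP Section 9.1 repeats this, and neither rule depends on the reason for leaving. SAP Section 6.4 rules out imputation. Protocol Section 9.2 sized the trial on independent exponential censoring of about 20% within 240 hours.

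**A second SAP rule.** SAP Section 9.1 also sets the GI2 time to missing when any of its three component times is missing, and SAP Section 5.1 ties mITT membership to all three components. A patient withdrawn before GI2 could therefore be dropped instead of censored.

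**The concern.** A safety reason can justify stopping study treatment. It is less clear why it should end the recording of meals and bowel movements, which is done in hospital or through the daily contact after discharge that Section 8.1.1.1 already sets up.

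Patients withdrawn for safety may well be those whose bowel function returns late. Kaplan-Meier censoring credits them with the recovery pattern of the patients still at risk. A shorter RMST is the better result, so the arm with more such withdrawals looks faster than it is. If withdrawals rise with dose, the error falls directly on the (-3, -1, 1, 3) contrast, in a trial meant to guide the choice of dose. None of the supplementary analyses in Protocol Section 9.4.5.1 or SAP Section 9.1.2 addresses informative withdrawal, and a GI2 time that was never collected can only be assumed afterwards.

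**Working it through.** **1. The planning figures.** Protocol Section 9.2 gives 44 per group for a 24-hour difference and 85 for an 18-hour difference, at 80% power and two-sided 0.05. The formula is

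n = (z0.975 + z0.80)² × Σ(c² × V) / (Σ c × μ)²

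where V is the per-patient variance of the RMST estimate. For a linear trend with total difference D, the contrast is 10D/3, that is 80 for D = 24 and 60 for D = 18. Also Σc² = 20 and (1.960 + 0.842)² = 7.85. With a common V:

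- 24 h: 44 = 7.85 × 20 × V / 6,400, so V is about 1,794 (SD about 42 h).
- 18 h: 85 = 7.85 × 20 × V / 3,600, so V is about 1,949 (SD about 44 h).

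The two figures agree with each other. They cannot be rebuilt outright, because the Weibull parameters are not given. Over an assumed grid (placebo RMST 100 to 150 h, shape 1.5 to 3.5, 20% censoring), n runs from 23 to 152 for 24 h and from 43 to 274 for 18 h. Placebo RMST 120 h with shape 3 gives 44.9 and 83.8, close to both, so that shape and a 120 h mean were used below.

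**2. Simulation of the follow-up rule.** Assumptions: no true treatment effect; in every arm 15% of patients have a complication that delays GI2; safety withdrawal occurs at 24 to 96 h, and its rate rises evenly from placebo to 5 mg; 2,500 runs per scenario. The table shows the 5 mg minus placebo RMST difference in hours, with the rejection rate of the trend test in brackets. Each cell gives n = 44, then n = 85.

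| Withdrawn, placebo to 5 mg | Delay of GI2 | Censored at withdrawal | Followed to GI2 or 240 h |
|---|---|---|---|
| 0 to 5% | 48 h | -1.8 (5.8%); -1.9 (6.1%) | -0.1 (5.2%); -0.1 (5.3%) |
| 0 to 5% | 120 h | -4.3 (6.0%); -3.9 (7.0%) | -0.2 (4.9%); 0.2 (4.6%) |
| 0 to 5% | not reached by 240 h | -4.7 (7.6%); -4.9 (9.3%) | 0.3 (5.6%); 0.0 (5.1%) |
| 0 to 10% | none | 0.1 (5.6%); -0.1 (5.2%) | 0.1 (5.8%); -0.1 (5.0%) |
| 0 to 10% | 48 h | -3.4 (7.4%); -3.8 (9.0%) | 0.2 (6.5%); -0.2 (5.4%) |
| 0 to 10% | 120 h | -8.8 (13.4%); -9.1 (22.8%) | 0.0 (5.1%); -0.4 (4.9%) |
| 0 to 10% | not reached by 240 h | -10.7 (16.7%); -10.7 (26.5%) | -0.4 (5.4%); -0.3 (5.2%) |

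With 5% withdrawn in every arm, the censored difference stays within 0.4 h of zero at every delay. Monte Carlo error is about 0.4 percentage points near 5% and up to 0.9 points at the highest rates.

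**3. If these patients are dropped instead of censored.** For the 0 to 10% gradient with some delay, the difference is -4.3 to -11.6 h. The extreme case can be checked by hand. The true 5 mg mean is 0.85 × 120 + 0.15 × 240 = 138 h. After dropping 10%, all from the complicated patients, it is (0.85 × 120 + 0.05 × 240) / 0.90 = 126.7 h. The shift is -11.3 h, against -11.6 h simulated.

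**4. Limits.** The simulation is unstratified and leaves out the 20% background censoring, so it shows direction and order of size only.

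**The case against.** The case against is strong on reach, and most of it stands.

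- **Most complications do not open the gap.** The triggers in Protocol Section 7.1, for example "There is any sign or symptom suggestive of gastrointestinal perforation, as assessed by the investigator", require stopping study treatment, not leaving the study. Section 8 frames safety concerns the same way, and Appendix 5 allows patients with a liver event to stay for follow-up. All of these patients remain under GI2 follow-up. The gap opens only if the investigator goes further and withdraws the patient from the study. Section 7.2 permits that but does not direct it.
- **The operative sentence is in Section 8.1.1.1.** It applies to withdrawal for any reason; Section 7.2 only supplies the safety route into it.
- **No contradiction with Section 9.4.5.1.** A reader might infer one from "Patients will continue to be evaluated for efficacy regardless of treatment adherence". That sentence concerns being off drug, and study withdrawal is a separate case.
- **No general loss of safety data.** A reader might infer this too. Withdrawn patients still have an End-of-study Visit (Section 4.1), adverse events are collected until then (Section 8.3.1) and followed to resolution or stabilization (Section 8.3.3).
- **The size is conditional.** The documents give no safety-withdrawal rate, no imbalance between arms and no recovery delay. More withdrawals on placebo would bias against naldemedine.

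What remains is that nothing provides for GI2 recording after the ET Visit once a patient is withdrawn from the study, and that the analysis then treats the censoring as uninformative.

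**Conclusion.** The point holds as a limited gap in data collection that should be closed. It does not show that the results will be biased.

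Bias needs two things together: safety withdrawal from the study that differs by arm, and later recovery in those withdrawn. Under the assumed gradients the spurious 5 mg minus placebo difference is about -2 to -5 h (0 to 5%) or -3 to -11 h (0 to 10%). Against the planned effects, the 0 to 10% range runs from 3.4/24 = 14% to 10.7/18 = 59%. If either condition fails, the bias is about zero.

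It would also be too strong to say that continued follow-up removes every assumption. Patients who withdraw consent would still be censored. A patient followed to 240 hours without GI2 could still be lost under the missing-component rule in SAP Section 9.1 and the mITT wording in SAP Section 5.1. Follow-up corrects the estimate only if the censoring rule prevails for those patients.

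**What to change.** 1. **Protocol Section 8.1.1.1, with a cross-reference in Section 7.2.** State that, unless consent is withdrawn, GI2 status continues to be recorded to 240 hours (Day 10) whatever the reason for withdrawal, from the chart in hospital or through the existing daily contact after discharge, with no other study procedure required. Limit the ET-only GI2 record to withdrawal of consent. The investigator's discretion to withdraw a patient for safety is left as it is.
2. **SAP Sections 5.1 and 9.1.** Reconcile the missing-component rule, the mITT definition and the censoring rule, so that a patient followed without GI2 stays in the mITT Population and is censored at the last assessment or at 240 hours, not set to missing.

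The cost is a short amendment, a SAP clarification before unblinding, and a few days of extra recording in a small number of patients.

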7.3 Lost to Follow-up

A patient will be considered lost to follow-up if he or she fails to return for the End-of-study Visit and is unable to be contacted by the hospital or doctor's office staff (ie, does not respond to at least 2 telephone calls, 1 e-mail, and a registered letter).

The following actions must be taken if a patient fails to return to the hospital or doctor's office for the End-of-study Visit:

- Before a patient is deemed lost to follow-up, the investigator, or qualified designee must make every effort to contact the patient and reschedule the missed End-of-study Visit as soon as possible. Contact will include at least 2 telephone calls, at least 1 e-mail, and a registered letter. The contact attempts should be within 30 days of the missed End-of-study visit and be documented in the patient's medical record.
- Should the patient continue to be unreachable by the above methods, he/she will be considered lost to follow-up.

8. STUDY ASSESSMENTS AND PROCEDURES

- Study procedures and their timing are summarized in the SoA. Protocol waivers or exemptions are not allowed.
- Adherence to the study requirements, including those specified in the SoA, is essential and required for study conduct.
- All Screening evaluations must be completed and reviewed to confirm that potential patients meet all eligibility criteria. The investigator or qualified designee must maintain a screening log to record details of all patients screened and to confirm eligibility or record reasons for screen failure, as applicable.
- Procedures conducted as part of the patient's routine clinical management (eg, physical examination, blood count, electrocardiogram [ECG]) and obtained before signing of the ICF may be utilized for Screening or Baseline purposes provided the procedures meet the protocol-specified criteria and are performed within the time frame defined in the SoA.
- Safety concerns should be discussed with the CRO immediately upon occurrence or awareness to determine if the patient should continue or discontinue study treatment.

8.1 Efficacy Assessments

8.1.1 Primary Efficacy Assessments

8.1.1.1 Time from End of Surgery to Time to First Toleration of Solid Food and First Bowel Movement

The time from the end of surgery (defined as the time the patient leaves the operating room) to time to first toleration of solid food (defined as the time when the patient consumes a meal that requires chewing and has no significant nausea or vomiting, as per the judgment of the investigator, for 4 hours after that solid food) and first bowel movement (GI2) will be recorded in the eCRF. First toleration of solid food and first bowel movement will be recorded until the patient meets the primary endpoint described above. If the patient discontinues study treatment, the patient still needs to be followed for GI2 until the achievement of this endpoint or until he/she completes the study. If the patient is withdrawn from the study, first toleration of solid food and first bowel movement, as applicable, will be recorded at the ET Visit (see also [Section 9.4.5.1](#)). If a patient is discharged from the hospital prior to having a first bowel movement, the reason for discharge prior to having the first bowel movement will be recorded in the eCRF. Additionally, the patient will be instructed to inform the investigator or qualified designee by phone, text, or e-mail within 24 hours of having a first bowel movement up to and including Day 10. The investigator or qualified designee will communicate (phone, text, or e-mail) with the patient daily up to and including Day 10 to record when the first bowel movement occurred.

8.1.2 Secondary Efficacy Assessments

8.1.2.1 Time from End of Surgery to Time When the Discharge Order is Written

The time from the end of surgery (as defined for the primary endpoint) to the time when the discharge order is written will be recorded in the eCRF (see also [Section 9.4.5.2](#)).

8.1.2.2 Reinsertion of the Nasogastric Tube

Whether a patient requires reinsertion of the nasogastric tube at any time during the postoperative treatment period will be recorded in the eCRF as yes or no along with the duration of the reinsertion (if applicable).

8.1.2.3 Readmission within 30 Day After Hospital Discharge

Whether a patient is discharged by Day 10 and then readmitted for any reason within 30 days after discharge will be recorded in the eCRF as yes or no, along with the reason why the patient is readmitted (if applicable).

8.1.3 Exploratory Efficacy Assessments

8.1.3.1 Time from End of Surgery to Discharge Readiness

The time from the end of surgery (as defined for the primary endpoint) to the time to discharge readiness (defined as GI recovery based on the clinical judgment of the investigator) will be evaluated and recorded in the eCRF.

8.1.3.2 Time from End of Surgery to Time of Actual Discharge

The time from the end of surgery (as defined for the primary endpoint) to time of actual discharge (departure) from the hospital will be recorded in the eCRF.

8.1.3.3 Prolonged Hospital Stay Due to Gastrointestinal Dysfunction

Prolonged hospital stay (defined as hospitalization for ≥ 7 days postoperatively) due to GI dysfunction will be recorded in the eCRF.

8.1.3.4 Patients Who Achieve GI2 in Each Treatment Group By Postoperative Day

The postoperative day for achievement of GI2 will be recorded in the eCRF.

8.1.3.5 Patients Who Receive Concomitant Medication That May Have a Laxative Effect

Any concomitant medication that may have a laxative effect will be recorded in the eCRF.

8.1.3.6 Effect of Prior Surgery on G12 Endpoint

The effect of prior surgery (yes/no) on the GI2 endpoint will be assessed.

8.2 Safety Assessments

Safety assessments will include recording of adverse events (AEs), including those that are serious and those that result in discontinuation of study treatment; clinical laboratory test results; vital signs measurements; 12-lead ECG findings; physical examination findings; postoperative pain, as assessed on the Numerical Pain Rating Scale (NPRS); and the administration of intra-operative and postoperative opioid analgesics.

Planned time points for all safety assessments are provided in the SoA.

For any abnormal laboratory test results (defined as hematology or blood chemistry values outside the reference range) or other safety assessments (eg, physical examination, vital signs, ECGs) that worsen from baseline following exposure to study treatment, the investigator will consider whether those results are clinically significant. For test results that are abnormal at baseline and significantly worsen (as per the judgment of the investigator) following the initiation of the study, the investigator must also consider whether those results are clinically significant. Any test result that is considered by the investigator or qualified designee to be clinically significant is to be recorded in the eCRF as an AE. If an abnormal laboratory finding is associated with disease or organ toxicity, the investigator should report only the disease or organ toxicity as an AE.

The investigator will consider test results to be clinically significant in the following circumstances:

- Test results lead to any of the outcomes included in the definition of a serious adverse event (SAE) (see [Section 8.3](#)).
- Test results lead to a change in study treatment administration or discontinuation from the study.
- Test results lead to a concomitant drug treatment or other therapy.
- Test results require additional diagnostic testing (except for a confirmatory test) or other medical intervention.
- Test results meet the management and stopping criteria for abnormal liver function tests identified in [Section 7.1](#) and [Appendix 5](#). When any test result meets the management and stopping criteria for liver function abnormalities ([Section 7.1](#) and [Appendix 5](#)), the results of further assessments and required follow-up should be recorded in the Liver Event Form.

In addition, the investigator should use his or her judgment in assessing the clinical significance of test results.

